4.4.4 Choice of control

The placebo control for Ad26.Mos4.HIV and Clade C gp140 is sodium chloride for injection, 0.9%.

4.4.5 HIV-1 incidence estimates from previous clinical trials among at-risk study populations in Southern Africa

The high rates of HIV acquisition amongst young women in Southern Africa highlight the need for biomedical interventions that are female controlled. Recent longitudinal studies evaluating various interventions indicate HIV incidence rates of between 4-11% and are summarized below:

Vaccine efficacy studies

• The HVTN 503 (Phambili) HIV vaccine study (2007), in which HIV-1 incidence among placebo recipients, 18-35 years of age was estimated at 3.7 per 100 person-years (5.86 for females and 1.93 for males) [33].

Topical and Systemic Pre-Exposure Prophylaxis Studies

- The FACTS 001 vaginal microbicide study (2011-2014), in which HIV-1 incidence was estimated at 4.0 per 100 person-years in women age 18-30 [34].
- The VOICE study of vaginal microbicide and systemic prophylactic antiretroviral drugs (2009-2013), in which overall HIV-1 incidence was 5.7% and incidence in the 3 placebo arms of the trial varied from 4.2 to 6.8 per 100 person-years, while the annual incidence in single women in South Africa aged 25 or younger was up to 10% [35].
- The MTN-020-ASPIRE dapivirine vaginal ring study (2012-2015), in which HIV-1 incidence was estimated at 4.5 per 100 person-years in female placebo recipients aged 18-45 in Malawi, South Africa, Uganda, and Zimbabwe [36].
- The RING study (IPM-027), a vaginal ring study (2012-2015), in which HIV-1 incidence was estimated at 6.1 per 100 person-years in female placebo recipients aged 18-45 [37].
- The Fem-PrEP, a study of PrEP effectiveness in HIV-negative women in Kenya, South Africa, and Tanzania (2009-2012), in which HIV-1 incidence was estimated at 5.0 per 100 person-years overall and ranged from 3.4–6 per 100 person-years in South African female placebo recipients aged 18-35 [38].

Based on a synthesis of the above references the estimated annual incidence rate of HIV-1 in Sub-Saharan women is 5.0% (total HIV acquisition events divided by total person years at risk). Under an assumed 90% PrEP efficacy during PrEP use, a conservative estimate of 4.2% annual HIV incidence can tolerate up to 15 out of 100 person years at risk during PrEP use.

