A conservative estimate of the background HIV-1 incidence is 4.2 per 100 person-years, and this level of incidence is expected for the duration of our study. Self-reported risk has been shown to decline over time in HIV prevention studies, attributed to risk reduction counseling and the provision of other interventions provided to study participants as part of a package of prevention. While incidence of HIV infection may be expected to decrease over time in trial populations due to the provision of HIV prevention packages, as well as the heterogeneity in risk for HIV-1, the increasing access to pre-exposure prophylaxis at a country level may impact HIV incidence more profoundly.

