## 10.2 Monitoring of the Use of PrEP

The use of oral FTC/TDF as PrEP (either off-study or provided in the study) may impact study outcomes (e.g., by lowering the HIV-1 incidence rate rendering a loss of statistical power). Dried blood spot (DBS) samples will be used for assessment of quantitative concentrations of intracellular tenofovir diphosphate (TFV-DP).

The prevalence of oral FTC/TDF use will be estimated and reported both as any detectable use and as effective use. More specifically, estimated percentages of person-years at-risk (PYR) during any detectable FTC/TDF use and during inferred effective FTC/TDF use will be reported.

Next we summarize how inferred effective use is measured. Current knowledge about PrEP in women indicates that consistent use of 6–7 doses a week is required to achieve protection. The lower quartile of simulated TFV-DP levels in DBS at 6 doses per week is 1064 fmol/punch (Castillo-Mancilla et al., 2013). In this trial, we will use 1,000 fmol/punch as the cut-off to define effective PrEP use based on the lower quartile cited above. Ongoing work with calibration of DBS from directly observed dosing studies may refine these thresholds. PrEP use measures will be reported by arm to the DSMB; in addition, both the OC and the protocol team leadership will see pooled estimates of FTC/TDF use.

DBS samples will be collected and stored for prospective monitoring of PrEP use at all study sites at pre-specified fixed sample collection days each month (see Section 10.2.1 for details). Furthermore, in order to increase the precision of PrEP use estimation, the frequency of sample collection may be increased.

At a given calendar time  $T$  (e.g., a fixed date prior to a scheduled DSMB meeting), we are interested in the population-level parameter, the percentage of person-years at-risk for HIV infection on effective PrEP use between initiation of DBS sample storage and time  $T$ . The definition of this parameter assumes that we have an assay readout from stored samples that accurately measures effective PrEP use as a binary outcome at the time the sample was drawn; importantly, it does not require an accurate measurement of effective PrEP use the day before or for any period of time earlier than the sampling day. In addition to estimating the percentage of person-years at risk on effective PrEP use, we define a similar parameter,

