the percentage of person-years at risk exposed to detectable PrEP using the lower limit of quantitation (LLOQ) of the DBS assay.

Define the target parameter of interest as

$$\Phi(T) = \frac{\int_{T_0}^T p(t) E[Y(t)] dt}{\int_{T_0}^T E[Y(t)] dt}$$

where  $T_0$  is the time since the first person enrolled after DBS storage commenced,  $p(t)$  is the percent of participants on effective PrEP use at time  $t \in [T_0, T]$ , and  $E[Y(t)]$  is the expected number of participants with DBS storage at-risk for HIV at time  $t$ .

We estimate  $\Phi(T)$  based on the binary PrEP use readout from the DBS assay and the DBS sampling plan. Let  $i$ , ranging from 1 to  $N$ , index study participants and let  $j$ , ranging from 1 to  $M_i$ , index participant DBS collection dates that are sampled for assaying. For each sample collected, we have an indicator  $x_{ij}$  of effective PrEP use which is only measured if the DBS sampling indicator,  $\Delta_{ij}$ , is equal to 1. The estimated percentage of person-years at risk on effective PrEP use from the initiation of PrEP monitoring time  $T_0$  until time  $T$  is defined as

$$\hat{\Phi}(T) = \frac{\sum_{i=1}^N \sum_{j=1}^{M_i} \Delta_{ij} x_{ij} \pi_{ij}^{-1} P_{ij}}{\sum_{i=1}^N \sum_{j=1}^{M_i} P_{ij}}$$

where the sampling probability,  $\pi_{ij}$ , and person-years,  $P_{ij}$ , are defined below.

Let  $k$ , ranging from 1 to  $K$ , index the DBS sampling plan collection intervals  $[T_0, T_1]$ ,  $(T_1, T_2]$ ,  $\dots$ ,  $(T_{K-1}, T_K]$  where the right endpoint of each interval is a sample collection date (with  $T_K \equiv T$ ) and define  $\mathcal{T}_k$  as the  $k^{\text{th}}$  interval. Let  $t_{i1} < t_{i2} < \dots < t_{iM_i}$  be the sampling times in  $[T_0, T]$  for the  $i^{\text{th}}$  participant and define  $t_{i0}$  as the maximum of  $T_0$  and the  $i^{\text{th}}$  participants enrollment time. The DBS sampling plan determines which samples, collectively across participants, will be assayed for PrEP use. Define the set of samples,  $S_{ij}$ , as all samples collected during the same collection interval  $\mathcal{T}_k$  as the sample  $i, j$ . That is,  $S_{ij} \equiv \{i', j' | t_{i'j'} \in \mathcal{T}_k \text{ for } k \text{ s.t. } t_{ij} \in \mathcal{T}_k\}$ . Define the sampling probability as

$$\pi_{ij} \equiv \frac{\sum_{i', j' \in S_{ij}} \Delta_{i'j'}}{|S_{ij}|}$$

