where  $|S_{ij}|$  is the number of samples in set  $S_{ij}$ . Define person-years,  $P_{ij}$ , as  $t_{ij} - t_{i(j-1)}$ . Note that our parameter of interest can be defined and estimated for the entire study cohort as well as for subregions (e.g., South African sites). We will report bootstrap 95% confidence intervals for  $\Phi(T)$ .

The same approach is used for point and confidence interval estimation of the percentage of person-years at risk exposed to detectable PrEP use.

An example of PrEP use report statistics are shown in Table 7.

Table 7: Summary of detectable and effective PrEP use

Number of DBS specimens collected over the 1 st batch period	$N_1$
Number of DBS specimens assayed over the 1 st batch period	$N_2$
Proportion of assayed specimens with TFV-DP above LLOQ (95% CI)	$N_3/N_2$ (x.xx, x.xx)
Proportion of assayed specimens with TFV-DP above effective use threshold* (95% CI)	$N_4/N_2$ (x.xx, x.xx)
Percent person-years on detectable PrEP through date T=xx (95% CI) #	$\widehat{\Phi}(T)_d$ (x.xx, x.xx)
Percent person-years on effective PrEP through date T=xx (95% CI) #	$\widehat{\Phi}(T)_e$ (x.xx, x.xx)
Repeat through N th batch period	

\*1000 fmol/punch

# $\widehat{\Phi}(T)_d$  is an estimate of the target parameter of interest based on measured TFV-DP above the LLOQ. Similarly,  $\widehat{\Phi}(T)_e$  is based on TFV-DP above the 1000 fmol/punch threshold for effective PrEP use.

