### 10.2.1 Simulation Study for PrEP Monitoring

A simulation study was conducted to help determine the DBS sampling schedule and, subsequently, the number of DBS samples that should be collected and assayed to achieve sufficient precision of estimation of the target parameters of interest. For a simulated trial, the PrEP monitoring plan was implemented based on the following assumptions: 1) enrollment falls randomly between Monday and Friday; 2) follow-up visits are scheduled on a randomly selected weekday during the week of the target visit date; 3) missed visits are distributed uniformly at a rate of 10%; 4) the dropout rate is 0.1/PYR in both treatment arms based on an exponential distribution; 5) the HIV infection rate in the placebo arm is 0.042/PYR based on an exponential distribution; and 6) initiation of DBS sample collection begins as of November 1, 2017. PrEP use was simulated at various constant rates among trial participants, and, for each rate, a random sample of participants is assumed to be continually on PrEP during the entire follow-up period. Simulation results are presented for the number of samples collected spaced at 6 month intervals. The intervals are spaced such that the last collection time point is approximately 3.5 months prior to the next DSMB meeting to allow the intracellular TFV-DP assay to be run and a report generated. In this simulation, the following three DBS sampling schedule scenarios are considered:

- S1. all samples are collected and assayed from visits held on a business day closest to the 15th of each month,
- S2. all samples are collected and assayed from visits held on business days closest to the 1st and the 15th of each month,
- S3. all samples are collected and assayed from visits held on business days closest to the 1st, the 10th, and the 20th of each month.

Simulation results for DBS sampling schedules S1–S3 are shown in Figures 1–3, respectively. For 6-monthly intervals shown on the x-axis, all samples assayed cumulatively through the

end of the month are used to estimate PrEP use prevalence from the beginning of DBS sample collection until the given timepoint using the estimator described in Section 10.2.

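### The PrEP person-time estimator in SAP 10.2 carries each blood-spot reading back to the previous spot or to enrollment, so it reads too high when PrEP use is rising and too low when it is falling

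*SAP*

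**What the plan says.** SAP 10.2 defines the target Phi(T) as the integral of p(t)E[Y(t)] over calendar time divided by the integral of E[Y(t)]. Here p(t) "is the percent of participants on effective PrEP use at time" t, and Y(t) counts the women at risk. The section adds: "The definition of this parameter assumes that we have an assay readout from stored samples" that correctly classifies use when the sample was drawn, and notes that "it does not require an accurate measurement of effective PrEP use the day before or for any period of time earlier". Both remarks concern the parameter.

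The estimator sums reading x_ij times P_ij (divided by the sampling probability) and divides by the sum of P_ij. P_ij is the time from the woman's previous spot to the current one. For a first spot, the SAP tells us to "define $t_{i0}$ as the maximum of $T_0$ and the $i^{\text{th}}$ participants enrollment time".

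SAP 10.2.1 adopts schedule S2: every spot from visits on the business days nearest the 1st and 15th of each month is collected and assayed. In the supporting simulation, PrEP use is at a constant rate and "a random sample of participants is assumed to be continually on PrEP during the entire follow-up period". Protocol 4.4.5 expects that "the increasing access to pre-exposure prophylaxis at a country level may impact HIV incidence more profoundly", without giving a size or shape.

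**The concern.** A reading that describes one day is credited to months of earlier follow-up. A Month 24 spot that is a woman's first counts for 24 months; a day 0 spot counts for nothing. Time after a woman's last spot, and women with no spot, enter neither sum. Readings taken late in follow-up and late in calendar time therefore weigh more than the target allows. This is harmless only if past use equals present use.

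The figure goes by arm to the DSMB and pooled to the oversight body and protocol leadership. They would use it to judge whether a low HIV incidence reflects PrEP. SAP 8.3 refers to the same section for assessing PrEP use, so the estimator may also reach the reported results. The simulation behind S2 could not show the problem, because constant use is the one case in which it vanishes.

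**Working it through.** **The plan's own figure.** SAP 10.2.1 projects about 500 assayed samples by end May 2019 (S1), end December 2018 (S2) and end October 2018 (S3). A rebuild without a day 0 spot gives 447, 428 and 431 with 10% missed visits, and 501, 472 and 477 with none missed. Adding the Day 169 visit, with 10% missed, gives 543, 533 and 537. These bracket 500. The SAP does not list the visits it simulated, so an exact match is not possible. The documents state no bias figure.

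**Spots per woman.** S2 uses about 24 of 261 business days a year. With 10% missed visits, the chance that a visit yields a spot is q = 0.9 × 24/261 = 0.083. Eleven visits through Month 24 (Protocol Appendix G, omitting Day 169) give 11 × 0.083 = 0.91 spots, or about 0.8 after dropout.

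**Hand check.** Take complete follow-up and use rising linearly from 0 to 20% over 24 months since enrollment, so the target is 10%. Visits fall at v = 0, 3, 6, 7, 9, 12, 13, 15, 18, 21 and 24 months. If every reading were a first spot, its weight would be v:

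- Σv = 128 and Σv² = 2054
- estimate = 20% × 2054/(24 × 128) = 13.4%, a ratio of 1.34

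Allowing for earlier spots, the expected weight at visit k (numbered from 0) is g_k = Σ_{j<k} q(1−q)^(k−1−j)(v_k − v_j) + (1−q)^k v_k. The Month 24 weight falls from 24 to about 17 months and the estimate to 12.9%. The direction and rough size do not change.

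**Simulation.** Inputs:

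- 2,600 women; 14-month accrual, halved in the first 3 months (Protocol 6.4.1); 19 months as a sensitivity run
- Appendix G visits on a random weekday of the target week; 10% missed; dropout 0.10 per person-year; spots from 1 November 2017 (SAP 10.2.1)
- pooled incidence 0.033 per person-year (SAP 10.3.1); sampling probability 1, because S2 assays every spot; follow-up capped at Month 24

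The trends are assumptions. Calendar trends below run from the start of spot collection to the cut-off. Results for 14-month accrual:

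| Assumed trend | Cut-off | Target | SAP estimate | Relative bias | Difference (points) | Quarter-weighted |
|---|---|---|---|---|---|---|
| 5 to 15%, linear, calendar | Dec 2020 | 10.03% | 10.87% | +8% | 0.84 | 10.06% |
| 0 to 20%, linear, calendar | Jul 2019 | 13.12% | 15.04% | +15% | 1.92 | 13.15% |
| 0 to 20%, linear, calendar | Dec 2020 | 10.05% | 11.68% | +16% | 1.63 | 10.09% |
| 0 to 20%, quadratic, calendar | Dec 2020 | 5.89% | 7.58% | +29% | 1.69 | 5.95% |
| 0 to 20%, since enrollment | Jan 2019 | 3.50% | 5.48% | +57% | 1.98 | 3.18% |
| 0 to 20%, since enrollment | Dec 2020 | 9.55% | 12.19% | +28% | 2.64 | 9.49% |

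Constant 10% use gives no bias. A jump from 0 to 20% in July 2019 gives +27% to +50%. Falling use gives about -2% to -28%. When a linear calendar rise is spread to May 2021, the difference is smaller: +0.9 to +1.3 points for 0 to 20%, and +0.4 to +0.9 for 5 to 15%.

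The sampling SD in the three linear calendar rows is 0.98, 1.13 and 0.81 points. The bias there is 0.84/0.98 = 0.9, 1.92/1.13 = 1.7 and 1.63/0.81 = 2.0 SD. The SAP denominator covers only about 15 to 30% of person-time at risk.

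**The case against.** Four points on the other side have force.

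- Section 10.2 attaches no rule to this estimate. The enrollment and futility guidelines in SAP 10.3 rest on projected infection counts and estimated VE. This stands, and it limits the consequence to interpretation.
- SAP Table 7 also reports, per batch, the plain proportion of assayed specimens above each threshold. These are not carried back and were off by only about -2% to -5% under calendar-time rises. This stands, but they do not repair the person-time estimate. They would also disagree with it in the same table with no explanation.
- For the gradual, country-level change that the protocol describes, the error is one or two percentage points, on a figure reported with a confidence interval. That is fair. However, a bootstrap interval reflects sampling error and does not correct a shift in the centre.
- Section 10.2 allows more frequent collection, which would shorten the gaps. That reduces the problem only if it is done.

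Three stronger readings are tempting, and the documents do not support them. A reader might infer that the SAP contradicts itself, because it disclaims any need for past readings; that sentence describes Phi(T) and is true of Phi(T). A reader might attach one fixed percentage to the overstatement; no PrEP trajectory is given, so none follows. A reader might infer that a false crossing of 15 per 100 person-years would trigger action. The July 2019 row does read 15.0% against a target of 13.1%. But the protocol's remark that its incidence assumption "can tolerate up to 15 out of 100 person years at risk during PrEP use" explains a planning figure and is not a monitoring boundary.

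**Conclusion.** The estimator does not target the SAP's own parameter unless PrEP use is constant. Its direction of error follows from the formula: upward with rising use, downward with falling use. The size depends on trends that the documents do not supply. Across those tried it was about +7% to +57% for rising use and about -2% to -28% for falling use. Linear calendar-time rises gave about +7% to +18%, or roughly 0.5 to 1.5 points, reaching 1.9 where the rise is complete by an earlier cut-off. These are illustrations and not bounds; a shallower trend gives less.

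The defect concerns a descriptive monitoring figure. It touches neither the primary efficacy analysis nor any stopping boundary. It is still worth correcting, because the protocol itself expects PrEP access to grow and the figure is meant to explain low incidence.

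**What to change.** Replace the estimator in SAP 10.2 with the direct plug-in for Phi(T). In each calendar interval (month or quarter), take the proportion of assayed spots above the threshold and multiply it by the whole cohort's observed person-years at risk in that interval. Sum over intervals and divide by total person-years. Keep the bootstrap interval, resampling women. Rerun the SAP 10.2.1 simulation with rising and falling use, and state the remaining assumptions.

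The cost is SAP wording and a few lines of code; samples and assays are unchanged. Sparse intervals must be pooled. Bias is reduced but not removed. The quarterly version was off by about 0 to +3% for smooth calendar rises, -10% to -1% for rises with time since enrollment, and +3% to +8% after a mid-2019 jump. It stayed near +60% when the cut-off fell exactly at a jump.

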### 10.2.1 Simulation Study for PrEP Monitoring

A simulation study was conducted to help determine the DBS sampling schedule and, subsequently, the number of DBS samples that should be collected and assayed to achieve sufficient precision of estimation of the target parameters of interest. For a simulated trial, the PrEP monitoring plan was implemented based on the following assumptions: 1) enrollment falls randomly between Monday and Friday; 2) follow-up visits are scheduled on a randomly selected weekday during the week of the target visit date; 3) missed visits are distributed uniformly at a rate of 10%; 4) the dropout rate is 0.1/PYR in both treatment arms based on an exponential distribution; 5) the HIV infection rate in the placebo arm is 0.042/PYR based on an exponential distribution; and 6) initiation of DBS sample collection begins as of November 1, 2017. PrEP use was simulated at various constant rates among trial participants, and, for each rate, a random sample of participants is assumed to be continually on PrEP during the entire follow-up period. Simulation results are presented for the number of samples collected spaced at 6 month intervals. The intervals are spaced such that the last collection time point is approximately 3.5 months prior to the next DSMB meeting to allow the intracellular TFV-DP assay to be run and a report generated. In this simulation, the following three DBS sampling schedule scenarios are considered:

- S1. all samples are collected and assayed from visits held on a business day closest to the 15th of each month,
- S2. all samples are collected and assayed from visits held on business days closest to the 1st and the 15th of each month,
- S3. all samples are collected and assayed from visits held on business days closest to the 1st, the 10th, and the 20th of each month.

Simulation results for DBS sampling schedules S1–S3 are shown in Figures 1–3, respectively. For 6-monthly intervals shown on the x-axis, all samples assayed cumulatively through the

end of the month are used to estimate PrEP use prevalence from the beginning of DBS sample collection until the given timepoint using the estimator described in Section 10.2.

The results indicate that approximately 500 assayed samples are required to estimate PrEP use prevalence with adequate precision. This number of samples is projected to accumulate by the end of May 2019 under S1, by the end of December 2018 under S2, and by the end of October 2018 under S3. The gain in precision becomes limited after the number of assayed samples grows beyond 700 under S1 or beyond 1,000 under S2 or S3; however, continuing to assay samples over the course of the trial will allow estimation of temporal trends in PrEP use.

Based on these simulation results, the trial will follow the DBS sampling schedule S2 as defined above.

[figure not shown]

Figure 1: Estimates of PrEP use prevalence under DBS sampling schedule S1 considering three PrEP use scenarios (20%, 10% and 0% of PYRs). The total number of samples that would be assayed according to the simulation study is shown below each date on the x-axis. Estimates are shown as dots of varying color intensity corresponding to the three PrEP use scenarios. The color bands show 95% pointwise bootstrap confidence intervals.

[figure not shown]

Figure 2: Estimates of PrEP use prevalence under DBS sampling schedule S2 considering three PrEP use scenarios (20%, 10% and 0% of PYRs). The total number of samples that would be assayed according to the simulation study is shown below each date on the x-axis. Estimates are shown as dots of varying color intensity corresponding to the three PrEP use scenarios. The color bands show 95% pointwise bootstrap confidence intervals.

[figure not shown]

Figure 3: Estimates of PrEP use prevalence under DBS sampling schedule S3 considering three PrEP use scenarios (20%, 10% and 0% of PYRs). The total number of samples that would be assayed according to the simulation study is shown below each date on the x-axis. Estimates are shown as dots of varying color intensity corresponding to the three PrEP use scenarios. The color bands show 95% pointwise bootstrap confidence intervals.

